### **Dose Interruption**

For elranatamab, an interruption is defined as a continuous missed scheduled dose (ie. 0mg dose) based on the planned dosing frequency (QW, Q2W, CCI).

For nirogacestat, an interruption is defined as a 0 mg dose administered on 1 or more days. (Note: A dose interruption is not considered a dose reduction).

What follows defines how dose interruptions of nirogacestat will be counted in the case of multiple dose interruptions:

- If an interruption occurs consecutively for at least 2 days due to the same reason, then it will be counted only once (example: If the actual dose on Days 1-3 is 100 mg BID and actual dose on Days 4-5 is 0 mg and dose interruption on Days 4-5 is due to AE, then the total number of dose interruptions is 1).
- If an interruption occurs consecutively for at least 2 days due to different reasons, then it will be counted for each reason (example: If the actual dose on Days 1-3 is 100 mg and actual dose on Days 4-5 is 0 mg and dose interruption on Day 4 is due to AE and dose interruption on Day 5 is due to dosing error, then the total number of dose interruptions is 2).
- If an interruption occurs for more than 1 day due to the same reason, but the days are not consecutive, ie, there is at least 1 dosing day in between, then each dose interruption will be counted as a different occurrence (example: if the actual dose on Days 1, 3, and 5 is 100 mg BID and actual dose on Days 2 and 4 is 0 mg, and dose interruptions on Day 2 and 4 are both due to dosing error, the total number of dose interruptions is 2).

For each of study treatment, the number and percentage of participants with dose interruptions as well as a breakdown of dose interruptions (1/2/3/ $\geq$ 4) will be summarized. In addition, the number and percentage of participants with at least 1 dose interruption due to AE will also be summarized. Percentages will be calculated based on the total number of participants in the Safety Analysis Set.

### **Dose Delay**

For elranatamab, a dose delay (regardless of reason) will be derived based on study drug administration date and will be grouped into the following categories based on the deviation of the actual to the planned treatment administration day (relative to the previous treatment administration date):

- No delay;
- 1-3 days delay;

- 4-6 days delay;
- 7 or more days delay (in the Q2W **CCI** schedule).

**CCI**

The number and percentage of participants with delayed study drug administration and maximum length of delay, ie, the worst case of delay if participants have multiple dose delays will be summarized by cohort, as applicable.

Dose delay is not applicable to nirogacestat.

#### **6.6.4. Concomitant Medications and Nondrug Treatments**

See [Section 6.5.4 of the master SAP](#) for summaries of concomitant medications and nondrug treatments.

#### **6.6.5. Subsequent Anticancer Therapies**

See [Section 6.5.5 of the master SAP](#) for summaries of subsequent anticancer therapies.

#### **6.7. Safety Summaries and Analyses**

See [Section 6.6 of the master SAP](#) for safety summaries and analyses.

### **7. INTERIM ANALYSES**

#### **7.1. Introduction**

There are interim safety assessments and an interim analysis for futility planned for this sub-study.

For both Part 1b and Part 2 of the sub-study, an internal safety review team will review safety and tolerability data on an ongoing basis for the interim safety assessments.

For Phase 2 part of the sub-study, an interim analysis for futility will be conducted after the first 25 participants are treated and followed for at least 2 post-baseline disease assessments without holding participant enrollments. The interim analysis will be performed on the primary endpoint of ORR using the methodology described in [Section 6.1.2](#) by the Sponsor. The internal core study team will review and evaluate the efficacy data at the interim futility analysis.

#### **7.2. Interim Analyses and Summaries**

##### **7.2.1. Interim Safety Assessments**

An internal safety review team will review cumulative safety data during the study conduct. In addition, the incidence of the following events will each be monitored by the Sponsor throughout the study. The review results and decisions will be documented in the study TMF.

- Grade 3-4 CRS;

- Grade 3-4 ICANS;
- Grade 4 treatment-related non-hematologic events (excluding CRS and ICANS);
- Grade 3-4 treatment-related GBS/GB-like AEs;
- Grade 4 treatment-related sensory neuropathy/other IR neurologic AEs (excluding ICANS);
- Grade 3-4 treatment-related motor neuropathy;
- Grade 5 events.

If the number of participants observed to have such identified events exceeds a prespecified threshold, the study will be placed on a temporary enrollment hold by the Sponsor. During any temporary enrollment hold, no new participants can be enrolled, nor can any newly enrolled participants start study intervention. Participants who have already started study intervention may continue treatment only if the benefit/risk assessment for the participant is judged to be positive by the investigator in consultation with the sponsor.

The criteria for placing the sub-study on temporary hold for safety reasons are based on Bayesian posterior probabilities. Using a non-informative Beta (0.5, 0.5) prior distribution, if the number of participants observed to have Grade 3 or 4 CRS results in a  $\geq 0.80$  posterior probability that the true Grade 3 or 4 CRS rate exceeds 20%, the sub-study will be put on a temporary hold. Separate but similar criteria will be used for participants with Grade 3-4 ICANS and treatment-related Grade 4 non-hematologic events (excluding CRS and ICANS). [Table 7](#) summarizes the minimum number of participants with such identified events that would meet the above criteria.

**Table 7. Identified Events That Would Prompt Temporary Enrollment Hold**

Number of Evaluable Participants	10-13	14-18	19-22	23-26	27-80	31-35	36-39
Minimum number of participants with Grade 3-4 CRS events that would lead to a temporary enrollment hold	4	5	6	7	8	9	10
Minimum number of participants with Grade 3-4 ICANS events that would lead to a temporary enrollment hold	4	5	6	7	8	9	10
Minimum number of participants with Grade 4 treatment-related non-hematologic events (excluding CRS and ICANS) that would lead to a temporary enrollment hold	4	5	6	7	8	9	10

Prior distribution: Beta (0.5,0.5)

Criteria for 40+ or more evaluable participants will be calculated such that the sub-study will be put on temporary hold if the posterior probability that the true event rate exceeds 20% is greater than or equal to 0.80.

Evaluable participants are defined as those having an identified event or those without such an event who have been followed for at least 35 days from first dose.

\* The study will be put on temporary hold as soon as the minimum number of evaluable participants with the identified AEs has reached the threshold (eg, if there are 4 participants experiencing the identified AEs out of the first 6 evaluable participants, the study will be put on hold). A minimum of 4 events are required to trigger a temporary hold.

The criteria for placing the study on temporary hold for the following safety reasons are based on Bayesian posterior probabilities using a non-informative Beta (0.5, 0.5) prior distribution. Specifically,

- If the number of evaluable participants observed to have treatment-related Grade 3-4 GBS/GB-like AEs results in a posterior probability that the true rate of such events exceeding 3% is  $\geq 0.80$ , the study will be put on a temporary hold;
- If the number of evaluable participants observed to have treatment-related Grade 4 sensory neuropathy/other IR neurologic AEs (excluding ICANS) or treatment-related Grade 3-4 motor neuropathy results in a posterior probability that the true rate of such events exceeding 10% is  $\geq 0.80$ , the study will be put on a temporary hold.

Table 8 summarizes the minimum number of evaluable participants with such identified events that would meet the above criteria.

**Table 8. Minimum Number of Participants with Identified Treatment-Related Events That Would Prompt Temporary Enrollment Hold (GBS/GB-like AEs, Peripheral Neuropathy/IR Neurologic AEs)**

Number of Evaluable Participants	20-39	40-64	65-90	-	-	-	-	-	-
Minimum number of participants with Grade 3-4 treatment-related GBS/GB-like events that would lead to a temporary enrollment hold*	2	3	4	-	-	-	-	-	-
Number of Evaluable Participants	6-11	12-19	20-27	28-35	36-43	44-52	53-60	61-69	70-78
Minimum number of participants with Grade 4 treatment-related sensory neuropathy /IR neurologic AE (excluding ICANS) or Grade 3-4 treatment-related motor neuropathy events that would lead to a temporary enrollment hold**	2	3	4	5	6	7	8	9	10

Prior distribution: Beta (0.5,0.5).

Evaluable participants are defined as those who have received at least 1 dose of study treatment having an identified event or those without such an event who have been followed for at least 28 days from first dose.

\*The study will be put on temporary hold as soon as the minimum number of evaluable participants with the identified AEs has reached the threshold (eg, for GBS/GB-like AEs, if there are 2 participants experiencing the identified AE out of the first 10 evaluable participants, the study will be put on hold). A minimum of 2 events are required to trigger a temporary hold.

\*\* The study will be put on temporary hold as soon as the minimum number of evaluable participants with the identified AEs has reached the threshold (eg, if there are 2 participants experiencing the identified AEs out of the first 4 evaluable participants, the study will be put on hold).

In addition, the study will be put on temporary hold if any of the following criteria are met:

- 1 Grade 5 event of CRS (by ASTCT criteria);
- 1 Grade 5 event of ICANS (by ASTCT criteria);
- 1 Grade 5 treatment-related peripheral neuropathy or IR neurologic event;
- Any 2 treatment-related Grade 5 events (excluding CRS and ICANS and peripheral neuropathy/IR neurologic event).

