*** **Environmental or Occupational exposure:** AEs or SAEs associated with occupational exposure are reported to Pfizer Safety using the CT SAE Report Form.

- When an AE or SAE occurs, it is the responsibility of the investigator to review all documentation (eg, hospital progress notes, laboratory reports, and diagnostic reports) related to the event.
- The investigator will then record all relevant AE or SAE information in the CRF.
- It is **not** acceptable for the investigator to send photocopies of the participant's medical records to Pfizer Safety in lieu of completion of the Electronic Data Collection Tool/CT SAE Report Form/AE or SAE CRF page.
- There may be instances when copies of medical records for certain cases are requested by Pfizer Safety. In this case, all participant identifiers, with the exception of the participant number, will be redacted on the copies of the medical records before submission to Pfizer Safety.
- The investigator will attempt to establish a diagnosis of the event based on signs, symptoms, and/or other clinical information. Whenever possible, the diagnosis (not the individual signs/symptoms) will be documented as the AE or SAE.

090177e19f0abbfaApproved On: 31-Oct-2023 20:35 (GMT)

Assessment of Severity

- The investigator will make an assessment of severity for each AE reported during the study and assign it to 1 of the categories listed below (as defined by the NCI CTCAE v5.0 system). An event is defined as “serious” when it meets at least 1 of the predefined outcomes as described in the definition of an SAE, NOT when it is rated as severe.

GRADE	Clinical Description of Severity
1	MILD AE
2	MODERATE AE
3	SEVERE AE
4	LIFE-THREATENING; urgent intervention indicated
5	DEATH RELATED TO AE

An event is defined as “serious” when it meets at least 1 of the predefined outcomes as described in the definition of an SAE, NOT when it is rated as severe.

The severity of CRS and ICANS will be graded according to ASTCT criteria (Lee et al, 2019). See Section 10.12.

Assessment of Causality

- The investigator is obligated to assess the relationship between study intervention and each occurrence of each AE or SAE. The investigator will use clinical judgment to determine the relationship.
- A “reasonable possibility” of a relationship conveys that there are facts, evidence, and/or arguments to suggest a causal relationship, rather than a relationship cannot be ruled out.

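### A single fatal treatment-related non-hematologic event adds nothing to the Grade 4 hold count, so a safety hold that would have triggered had that participant survived at Grade 4 can be missed

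*SAP*

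**What the plan says.** Section 7.2.1 of the Sub-study A SAP lists the events to be monitored. Two separate items are "Grade 4 treatment-related non-hematologic events (excluding CRS and ICANS" and "Grade 5 events".

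The first is monitored through Table 7, in the row headed "Minimum number of participants with Grade 4 treatment-related non-hematologic events (excluding CRS and ICANS) that would lead to a temporary enrollment hold". Enrollment is held "if the posterior probability that the true event rate exceeds 20% is greater than or equal to 0.80", under a Beta(0.5, 0.5) prior and with a floor of 4 events. Sub-study B (7.2.1, Table 6) and the master SAP (7.2.1, Table 6) carry the same row with a cut-off of 0.90.

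Fatal events have their own list below the tables. In the two sub-study SAPs, one Grade 5 CRS, ICANS or treatment-related neurologic event is enough for a hold. For the rest the rule is "Any 2 treatment-related Grade 5 events (excluding CRS and ICANS and peripheral neuropathy/IR neurologic event"). The master SAP has the single-event rules for CRS and ICANS only, and needs two Grade 5 events across all other categories.

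The Protocol (10.3.3, Assessment of Severity) tells the investigator to grade each event and "assign it to 1 of the categories listed below". Grade 5 is "DEATH RELATED TO AE". No text says whether a participant with a Grade 5 event also counts in the Grade 4 row.

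**The concern.** Read literally, a fatal related non-hematologic event is not a Grade 4 event, so it never enters the row. If it is the only such death, it does not trigger the two-death rule either. A participant who moves from surviving a Grade 4 event to dying of it can therefore take the sub-study from hold to no hold. A prespecified safety trigger should not be switched off by a worse outcome.

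The denominator is also unclear. A participant is evaluable by having an identified event, or by being free of one with at least 35 days of follow-up. Someone who dies of such an event before day 35, with no Grade 4 event recorded, fits neither limb if the definition is applied row by row.

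**Working it through.** **Inputs.** From the SAPs, 7.2.1: prior Beta(0.5, 0.5); reference rate 20%; cut-off 0.80 (Sub-study A) or 0.90 (Sub-study B, master); floor of 4 events; hold at 2 other related Grade 5 events.

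**1. The plan's own table.** With r events in n evaluable participants,

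P(rate > 20%) = 1 − F(0.20; 0.5 + r, 0.5 + n − r),

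where F is the Beta distribution function. The threshold is the smallest r that reaches the cut-off. At 0.80 this gives 4, 5, 6, 7, 8, 9, 10 for n = 10-13, 14-18, 19-22, 23-26, 27-30, 31-35, 36-39. These are the Table 7 values, with the column printed as 27-80 reproducing only as 27-30. The Sub-study B and master tables reproduce at 0.90.

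**2. The example.** Three Grade 4 events and one Grade 5 event among 10 evaluable participants in Sub-study A:

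- Row as written: r = 3, n = 10, posterior 0.795. This is below 0.80, and 3 < 4.
- If the death is also dropped from the denominator: r = 3, n = 9, posterior 0.844, but still below the 4-event floor.
- Two-death rule: 1 < 2.
- Result: no hold.

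Had the fourth participant survived at Grade 4, r = 4 and n = 10 give 0.934, which is above both 0.80 and 0.90, and enrollment is held. The same pattern (3 + 1) gives no hold up to n = 13 in Sub-study A, where 4/13 gives 0.837.

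**3. Where it occurs.** Take every pair of Grade 4 and Grade 5 counts covered by the tables and turn one Grade 4 survivor into one death:

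- Sub-study A (n = 10-39): the hold switches off in 30 pairs and on in 180.
- Sub-study B and master (n = 8-34): off in 27, on in 164.

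The off cases number exactly one per n: the Grade 4 count sits on the threshold and there is no other death. The on cases all need one death to have occurred already. These are counts of configurations, not probabilities.

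**4. Size.** Participants are taken one at a time, with the hold checked after each and the floor and two-death rule applied throughout. The probabilities come from an exact recursion. The true rates and fatal shares are assumptions; the documents give none. N = 50 for Sub-study A is the planned Phase 2 size. For Sub-study B, N = 24 + 20 − 6 = 38 (5.1.1.1 and 5.1.1.2). At a true Grade 4-5 rate of 25%:

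| Sub-study | Fatal share | As written | Grade 4-5 in row | Gain (points) |
|---|---|---|---|---|
| A | 2% | 0.730 | 0.748 | 1.8 |
| A | 10% | 0.766 | 0.804 | 3.8 |
| A | 30% | 0.938 | 0.948 | 0.9 |
| B | 2% | 0.519 | 0.540 | 2.1 |
| B | 10% | 0.566 | 0.615 | 4.9 |
| B | 30% | 0.837 | 0.855 | 1.7 |

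A simulation of 40,000 trials of the A case at 10% fatal gave 0.77 and 0.81, which agrees within simulation error. Over true rates of 20, 25 and 30% and fatal shares of 2, 5, 10, 20 and 30%, the gain is 0.5 to 4.2 points in A and 1.4 to 4.9 in B. At a true rate of 10%, the extra holds amount to 0.3 to 0.9 points in A and 0.2 to 0.5 in B.

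**The case against.** The strongest reply is that this is a deliberate two-track scheme. The Bayesian rows stop at Grade 4 throughout, and Grade 5 is a separate item with a stricter rule: two deaths suffice at any n, against 4 to 10 Grade 4 events. A reader might infer from the gap that a death generally counts less toward a hold than a survived Grade 4 event. The documents do not support that, and step 3 shows the opposite in most configurations. In Sub-study A at a true rate of 25%, the hold probability as written is 0.744 with no fatal events, dips to 0.73 at 2-5% fatal, and then rises to 0.77, 0.87 and 0.94 at 10, 20 and 30%.

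A reader might also infer that the row is meant to measure life-threatening-or-worse toxicity. No text says so, and the Grade 4 and Grade 5 items are listed apart.

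Two further points are fair. An internal team reviews cumulative safety data, so a single death would not go unseen. And the SAPs do not say how an event recorded at Grade 4 that later proves fatal is counted; on one reading it enters both rules.

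All of this limits the point without removing it. The tally of 180 against 30 does not help with the first death, because a swap can switch a hold on only when another death has already happened. For the first one it can only remove a hold or change nothing. Ongoing review is a safeguard, but it is not the prespecified trigger.

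**Conclusion.** The concern holds in a narrow form. The row counts Grade 4 only, it never combines with the two-death rule, and a hold can therefore be missed when there is exactly one such death and the Grade 4 count is one short of the threshold. This rests on reading one grade per event literally.

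The effect on the overall hold probability is modest: about 0.5 to 4.2 points in Sub-study A and 1.4 to 4.9 in Sub-study B, under assumed true rates of 20-30% and fatal shares of 2-30%. The case for change is less the size than the direction, since a worse outcome can cancel a safety hold, and the correction is cheap.

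**What to change.** In Sub-study A 7.2.1 and Table 7, Sub-study B 7.2.1 and Table 6, and master SAP 7.2.1 and Table 6, reconcile the row with the Grade 5 rule:

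- Count participants whose worst treatment-related non-hematologic event (excluding CRS and ICANS) is Grade 4 or 5, each once.
- State that such a participant is evaluable for the row whatever the length of follow-up, so that an early death is in both numerator and denominator.
- Keep the separate Grade 5 rules, and say that a fatal event counts under both.

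The thresholds do not change, because they depend only on n, the prior, the reference rate and the cut-off. The cost is SAP wording and slightly more temporary holds, up to about 1 point at a true rate of 10%. Protocol Section 9 refers to the sub-study protocols for statistics. Those are not among the documents here; if they repeat the row, they need the same edit.

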### 7.2.2. Interim Analysis for Futility

For Phase 2 part of the study, an interim analysis for futility will be conducted on the first 25 participants enrolled and treated. The primary endpoint of ORR will be evaluated at this analysis using a futility boundary based on the predictive probability. More specifically, a combination may stop for futility if the predictive probability of observing  $\geq 38$  objective responses in 50 patients at the primary analysis based on the data observed at the interim analysis is  $< 0.05$ .

090177e1a0f4f44c\Approved\Approved On: 14-Jun-2024 22:12 (GMT)

The posterior beta-binomial predictive distribution for the number of responders in the second stage of the study is as follows:

$$\pi(r_2|IA.r, IA.n) = \binom{n_2}{r_2} \frac{B(r_2+a+IA.r, b+IA.n-IA.r+n_2-r_2)}{B(a+IA.r, b+IA.n-IA.r)}$$

where IA.r and IA.n denote the number of responses and number of participants at the interim analysis,  $r_2$  and  $n_2$  denote the number of responses and number of participants from the second stage of the study ( $n_2 = 25$ ), and B denotes the Beta function.

The futility boundary based on the posterior predictive distribution can be obtained using the exact method to calculate the probability of observing  $\geq 38$  objective responses in 50 participants at the primary analysis, ie,

$$P(IA.r + r_2 \geq 38|IA.r, IA.n) = \sum_{r_2=38-IA.r}^{n_2} \pi(r_2|IA.r, IA.n)$$

With 25 participants at the interim analysis, if there are  $\leq 16$  (64%) objective responses observed, further accrual may be stopped for the combination. Otherwise, the study will proceed as planned to the primary analysis as described in [Section 6.1.2](#).

The exact futility boundary will be updated prior to the time of the analysis based on the actual number of participants enrolled and treated in this sub-study.

## 9. APPENDICES

### 9.1. Appendix 1: BLRM Design CCI

This section provides the details of the statistical model, the derivation of prior distributions from historical data, the results of the Bayesian analyses and respective dosing decisions for some hypothetical data scenarios, and a simulation study of the operating characteristics of the model CCI

#### Statistical Model

The statistical model for dose-DLT data CCI

The monotherapy RP2D of elranatamab is 76 mg, which was determined in Study C1071001. In this sub-study, the initial dose level of elranatamab will be 4 mg with a priming dose of 4 mg for the first dose. The dose level of nirogacestat will remain at 100 mg BID.

CCI

CCI

**Description of the Meta-Analytic-Predictive Approach**

The aim of the MAP approach is to derive a prior distribution for the logistic parameters  $(\log(\alpha^*), \log(\beta^*))$  of the new trial using DLT data from historical studies. Let  $r_{ds}$  and  $n_{ds}$  be the number of participants with a DLT, and the total number of participants, respectively, at dose  $d$  in historical trial  $s$  ( $s = 1, \dots, S$ ). The corresponding probability of a DLT is  $\pi_{ds}$ . The model specifications are as follows:

CCI

090177e1a0f4f44c\Approved\Approved On: 14-Jun-2024 22:12 (GMT)

[figure not shown]
The historical trials are partitioned into  $\langle G \rangle$  exchangeability groups, with the exchangeability group membership of historical trial  $s$  being represented by  $g(s)$ . The new trial is assigned to exchangeability group  $g(*)$ . The parameter  $\mu = (\mu_1, \mu_2)$  is the mean for the logistic parameters, and  $\psi_g$  is the between-trial covariance matrix for exchangeability group  $g = 1, \dots, \langle G \rangle$ . Covariance matrix  $\psi_g$  is defined by the standard deviations  $(t_{g1}, t_{g2})$ , and correlation  $r$  (a common value for  $r$  is used across all groups). The parameters  $t_{g1}$  and  $t_{g2}$  quantify the degree of between trial heterogeneity for exchangeability group  $g$ . With different prior distributions for the parameter sets  $(t_{g1}, t_{g2})$  it is possible to allow for differential discounting for the historical strata. In this way the quality and relevance of historical data can be accounted for in the meta-analysis. The following priors will be used for these parameters:

The MAP prior for single-agent model parameters in the new trial,  $(\log(\alpha^*), \log(\beta^*))$ , is the predictive distribution

$$(\log(\alpha^*), \log(\beta^*)) \mid (r_{ds}, n_{ds} : s = 1, \dots, \langle S \rangle)$$

Since the predictive distribution is not available analytically, the Markov chain Monte Carlo (MCMC) method is used to simulate values from this distribution. This is implemented using Just Another Gibbs Sampler (JAGS) version 4.3.0.

**Table 9. Historical Dose Limiting Toxicity Data** CCI

CCI	Number of Participants	Number of Participants with DLTs
	6	0
	4	0
	4	0
	4	0
	6	0
	6	0

Abbreviations: CCI; DLT=dose limiting toxicity; CCI

CCI Priors for  $t_{1p}$  and  $t_{2p}$  are assigned such that (1) their medians correspond to moderate between-trial heterogeneity, and (2) their uncertainty (95% prior interval) cover plausible between-trial standard deviations.

The prior distributions for the model used for deriving the MAP priors are specified in Table 10.

**Table 10. Prior Distributions for the Parameters of the MAP Model Used to Derive the Prior** CCI

Parameter	Prior distribution
$\mu_{1p}$	N (mean = 0, sd =2)
$\mu_{2p}$	N (mean = 0, sd=1)
CCI	
$r_p$	Uniform (-1,1)

Abbreviations: N=normally distributed; sd=standard deviation.

